9.7.3 Complete Response Rate

Complete response rate (CRR) will be defined as the proportion of patients with a BOR of CR, according to the 2014 Lugano classification, as determined by the Investigator. The percentage of CRR with its 95% CI will be presented.

9.7.4 Relapse-free Survival

RFS will be defined among CR patients as the time from the earliest date of first complete response until the first date of either disease progression or death due to any cause. For patients who have not progressed or died at the time of the analysis, censoring will be performed using the date of the last valid disease assessment. The data will be analyzed by the Kaplan-Meier method. The median RFS and 95% CI will be presented. Further details will be outlined in the SAP.

9.7.5 Progression-free Survival

PFS will be defined as the time from first dose of study drug until the first date of either disease progression or death due to any cause. For patients whose disease has not progressed at the time of the analysis, censoring will be performed using the date of the last valid disease assessment. The data will be analyzed by the Kaplan-Meier method. The median PFS time and 95% CI will be presented. Further details will be outlined in the SAP.

9.7.6 Overall Survival

Median OS will be defined as the time from first dose of study drug until death due to any cause. For patients who have not died at the time of the analysis, censoring will be performed using the date the patient was last known to be alive. The data will be analyzed by the Kaplan-Meier method. The median OS and 95% CI will be presented. Further details will be outlined in the SAP.

9.8 Safety Analyses

Safety analyses will be presented descriptively.

9.8.1 Adverse Events

The focus of AE summarization will be on TEAEs. A TEAE is defined as an AE that occurs or worsens in the period extending from the first dose of study drug to 30 days after the last dose of study drug or initiation of new anti-cancer therapy (whichever occurs earlier).

TEAEs will be summarized. Summary tables will be presented to show the number of patients reporting TEAEs by severity grade and corresponding percentages. A patient who reports multiple TEAEs within the same Preferred Term (or System Organ Class [SOC]) is counted only once for that Preferred Term (or SOC) using the worst severity grade.

Separate summaries will be prepared for TEAEs classified as severe or life-threatening (Grade 3 or higher); study drug-related AEs; AEs leading to treatment interruption, modification, or discontinuation; serious AEs; and death.

9.8.2 Clinical Laboratory Results

Clinical hematology, coagulation panel, biochemistry, and urinalysis data will be summarized at each scheduled assessment. Shifts for clinical laboratory results that can be graded according to CTCAE v4.0 (or more recent) will be summarized by CTCAE grade. Shifts for other numeric laboratory results will be by high/normal/low flag. Shifts for all other laboratory results will be by normal/abnormal flag.

Summaries by visit will include data from scheduled assessments, and all data will be reported according to the nominal visit date for which it was recorded. Unscheduled data will be included in “worst-case post-Baseline” summaries, which will capture a worst case across all scheduled and unscheduled visits after the first dose of study drug. Further details will be provided in the SAP.

9.8.3 Additional Safety Assessments

The results of scheduled assessments of vital signs, physical examinations, ECOG performance status, and 12-lead ECGs will be summarized. All data will be reported according to the nominal visit date for which it was recorded (i.e., no visit windows will be applied). Unscheduled data will be included in “worst case” summaries, which will capture a worst case across all scheduled and unscheduled visits after the first dose of study drug. All data will be listed. Further details will be provided in the SAP.

9.9 Pharmacokinetic Analyses

The PK profile for loncastuximab tesirine in serum will include determination of maximum concentration (C_{max}), time to C_{max} (T_{max}), and area under the concentration-time curve from time zero to the last quantifiable concentration (AUC_{0-last}). [REDACTED]

[figure not shown]
PK parameters will be determined for all PK-evaluable patients using either a compartmental (population) or non-compartmental analysis method with Phoenix WinNonlin [REDACTED] or other appropriate software and may be reported separately.

Demographic data for the PK population will be summarized. Potential correlations of PK parameters to baseline characteristics and safety observations will be assessed but may be reported separately. In addition, the influence of loncastuximab tesirine PBD-conjugated antibody and unconjugated warhead SG3199 concentrations, if appropriate on the QTc interval will be assessed but reported separately.

9.10 Immunogenicity Analyses

A tiered immunogenicity strategy (Figure 2) will be undertaken to evaluate ADAs by screening and confirmatory assays with titer evaluation, followed by characterization and evaluation of neutralizing capacity as needed. ADA sample collection, banking, and testing in validated and to be validated assays will be according to the new FDA Draft Guidance for Industry (April 2016): ‘Assay Development and Validation for Immunogenicity testing of Therapeutic Protein Products’.

Figure 2 Anti-drug Antibody Tiered Immunogenicity Testing Strategy

Abbreviations: ADA, anti-drug antibody; ADC, antibody-drug conjugate; BSA, bovine serum albumin; mAb, monoclonal antibody; PK, pharmacokinetics.

Results from ADA testing will include tabular summarization for number/proportion of patients with positive pre-dose ADA response, number of patients with post-dose ADA response only, and number of patients with positive ADA response at any time. The denominator will be the total number of patients tested for ADAs in the study.

[REDACTED]

[REDACTED]

10 Data Management and Quality Assurance

The Investigator will maintain accurate source documentation including patient medical records, laboratory reports, ECG strips, and patient diaries.

Investigative site qualified personnel will enter patient data into an EDC system. The analysis data sets will be a combination of these data and data from other sources.

Clinical data management will be performed in accordance with applicable standards and data cleaning procedures to ensure the integrity of the data (e.g., removing errors and inconsistencies in the data). AEs will be coded using the Medical Dictionary for Regulatory Activities (MedDRA). Concomitant medications will be coded using the World Health Organization (WHO) Drug Dictionary.

After database lock, each study site will receive information about all of their site-specific eCRF data as entered into the EDC system for the study, including full discrepancy and audit history. Additionally, a copy of study data from all sites will be created and sent to the Sponsor for storage. The CRO will maintain a duplicate copy for its records. In all cases, patient initials will not be collected or transmitted to the Sponsor.

For detailed instruction on data entry procedures and timelines, please refer to the eCRF Completion Guidelines.

11 Ethical, Regulatory, and Study Management Considerations

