| 
 To evaluate the antitumor effect of the combination of loncastuximab tesirine with durvalumab To characterize the pharmacokinetic (PK) profile of loncastuximab tesirine when given in combination with durvalumab To evaluate the immunogenicity of loncastuximab tesirine when given in combination with durvalumab | 
 Overall response rate (ORR according to the 2014 Lugano classification as determined by the Investigator. ORR is the proportion of patients with a best overall response (BOR) of complete response (CR or partial response (PR) Duration of response (DOR defined as the time from the documentation of first tumor response to disease progression or death CR rate defined as the percentage of patients with a BOR of CR Relapse-free survival (RFS) defined as the time from the documentation of CR to disease progression or death Progression free survival (PFS) defined as the time between start of treatment and the first documentation of progression, or death Overall survival (OS) defined as the time between the start of treatment and death from any cause Concentrations and PK parameters of loncastuximab tesirine (total antibody, PBD-conjugated antibody, and unconjugated cytotoxin SG3199) Anti-drug antibody (ADA) titers and, if applicable, neutralizing activity to loncastuximab tesirine |
| 
[REDACTED]
 | 
[REDACTED]
 |

4 Study Design

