8.4.2 Immunogenicity

Detection of ADAs will be performed by using a screening assay for identification of antibody positive samples/patients, a confirmation assay, and titer assessment, and will be performed using the Meso-Scale Discovery Electrochemiluminescence (MSD-ECL) platform. If an ADA is confirmed, a functional assay for the assessment of the neutralizing capacity of the ADA will be performed.

Approximately 6 mL of whole blood will be collected as per [Table 1](#) and [Table 5](#). Blood should be drawn from a vein away from the one used for study drug infusion.

For patients who test positive for ADAs, an additional ADA sample will be requested for testing every 12 weeks following the EOT visit until the ADA titer falls to a background level.

ADA samples must be stored at $\leq -70^{\circ}\text{C}$. Please refer to the laboratory manual for detailed instructions regarding specimen handling and shipment.

[REDACTED]

[REDACTED]

[REDACTED]

9 Statistical Considerations

Full details of the analysis plan, including a more technical and detailed elaboration of the statistical analyses, will be provided in the statistical analysis plan (SAP). [REDACTED]

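### The ADA summary in protocol 9.10 uses no titers, so it cannot show a treatment-boosted response in a patient positive before dosing, and the visible SAP does not repair this

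*Protocol*

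**What the plan says.** Protocol Section 9.10 specifies three tabulated results from ADA testing: the "number/proportion of patients with positive pre-dose ADA response", the "number of patients with post-dose ADA response only", and the "number of patients with positive ADA response at any time". On the base for percentages it says "The denominator will be the total number of patients tested for ADAs in the study".

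Titers appear in three other places. The secondary endpoint in Protocol Section 3, Table 2 is "Anti-drug antibody (ADA) titers and, if applicable, neutralizing activity to loncastuximab tesirine". Section 8.4.2 describes a screening assay followed by "a confirmation assay, and titer assessment". The tiered strategy in 9.10 itself is to "evaluate ADAs by screening and confirmatory assays with titer evaluation".

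Samples are serial. Protocol Table 5 schedules ADA blood before dosing on C1D1, then on C1D15, C2D1, C3D1, Day 1 of Cycles 5 to 7 (only for patients given loncastuximab tesirine in Cycles 5 and 6) and EOT. Section 8.4.2 adds 12-weekly sampling after EOT for positive patients until the titer is back to background.

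SAP Section 2.2 keeps the immunogenicity objective. SAP Section 3.3 limits the analysis to Part 1 because the trial stopped early. The visible SAP contains no ADA table, listing or definition.

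**The concern.** A new response in a previously negative patient and a rise in an existing response are both ways in which treatment can affect immunogenicity. The visible summary shows only the first. A pre-dose positive patient cannot enter the post-dose-only category by definition, and the other two categories do not depend on what happens after dosing. The endpoint is worded as titers, and the protocol follows positive patients for the course of the titer, but the specified summary reduces everything to positive or negative.

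At stake is the completeness of one descriptive secondary result. The report could give the three planned counts correctly and still not say whether any pre-existing response was boosted on treatment.

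**Working it through.** The plan attaches no figure to this point, so there is none to reproduce. The check is a count of what the three categories can show.

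**Inputs.** The three categories and the denominator come from Protocol 9.10. The planned Part 1 size, about 15, comes from Protocol 9.1. The documents give no pre-dose positivity rate and no number actually tested.

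**Notation.** Of n patients tested, let k be positive before dosing and m positive only afterwards. Let b, from 0 to k, be the number of the k whose titer rises on treatment.

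**Step 1: what the planned summary shows.** Pre-dose positive = k. Post-dose only = m. Any time = k + m. None of the three contains b, and the third is the sum of the first two.

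**Step 2: illustration.** Assume n = 15, k = 3 and m = 1, with all 15 having a baseline and a later sample. These values are chosen only to show the mechanism. Treatment-emergent incidence, counting boosted cases, is (m + b)/n.

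| b | Pre-dose positive | Post-dose only | Any time | (m + b)/n |
|---|---|---|---|---|
| 0 | 3 | 1 | 4 | 1/15 = 6.7% |
| 1 | 3 | 1 | 4 | 2/15 = 13.3% |
| 2 | 3 | 1 | 4 | 3/15 = 20.0% |
| 3 | 3 | 1 | 4 | 4/15 = 26.7% |

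The planned columns are identical in every row.

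**Step 3: size per case.** Each boosted patient adds 1/n. At n = 15 this is 6.7 percentage points. The number tested is unknown. Three dose levels of 3 to 6 patients give 9 to 18 without replacements, so 1/9 = 11.1 to 1/18 = 5.6 points; early termination could leave fewer than 9.

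**Step 4: can such patients occur?** Exclusion criterion 1 removes only patients with a known history. The Schedule of Events has no ADA sample at screening, and the first is taken before dosing on C1D1. Protocol 9.10 has a category for pre-dose positives. They are therefore possible. Nothing in the documents says how common they are.

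**The case against.** The strongest reply is that the list in 9.10 is open. It begins "Results from ADA testing will include tabular summarization", which does not rule out further summaries. Redacted blocks follow, and the testing-strategy figure is not shown. Protocol Section 9 leaves full detail to the SAP, and SAP Section 4 says that important data will be listed. This stands in part. A reader might infer that boosted responses would never be reported, and the documents do not support that. They support only the narrower statement that no visible, specified table, listing or definition uses titers or identifies boosting.

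A reader might also scale the effect to the 75 patients planned for the whole study. That is not supported either: only Part 1 is analysed, and the documents give no pre-dose rate and no share of patients with a rising titer. Inclusion criterion 4 admits patients with prior CD19-directed therapy, but that does not show that they carry antibodies to this product.

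A third tempting reading is that the summary hides whether durvalumab raises immunogenicity. The objective is to evaluate immunogenicity of loncastuximab tesirine under the combination. The study is single-arm and plans no hypothesis tests, so no ADA table from it could by itself attribute a change to durvalumab.

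Finally, neither document defines a boosted response or a fold threshold, and the visible SAP has no ADA table to which a row could simply be added. Both are true. They bear on how the remedy is written, not on whether the gap exists.

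**Conclusion.** The point holds in limited form. The three visible categories cannot distinguish a pre-dose positive patient whose titer rises from one whose titer is flat or falls, although titers are the named endpoint and are collected serially. The visible SAP keeps the objective without supplying an analysis that closes the gap.

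The logical result needs no assumption about rates. The size does: it depends on how many patients were tested and how many were positive before dosing, and the documents state neither. In a Part 1 planned at about 15, few or no boosted cases may occur; if 15 are tested, each would move treatment-emergent incidence by about 6.7 percentage points. This is a free improvement to a descriptive secondary result, with no effect on any error rate or on the sample size.

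**What to change.** Add a short immunogenicity section to the SAP that does the following:

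- Defines baseline as the C1D1 sample taken before dosing. Protocol Table 5 also labels later samples as pre-dose, so this should be explicit.
- Defines treatment-induced ADA as positive only after dosing.
- Defines treatment-boosted ADA as positive at baseline with a later titer above a stated fold rise. The threshold should be fixed before titers are reviewed, for example from the assay's dilution step; the documents give no value.
- Reports treatment-emergent ADA as the sum of the two, among patients with a baseline and at least one post-baseline sample. A patient lacking either cannot be classified.
- Keeps the three counts in Protocol 9.10 alongside.
- Lists ADA status and titer by patient and visit. At this sample size the listing would show any rise directly, whatever threshold is chosen.

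The cost is one definition, one small table and one listing. No new sample, visit or assay is needed.

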11.1 Regulatory and Ethical Conduct of the Study

The study will be performed in accordance with the ethical principles that have their origin in the Declaration of Helsinki, International Council for Harmonisation (ICH) Good Clinical Practice (GCP), and all applicable regulations.

11.2 Independent Ethics Committee or Institutional Review Board

Federal regulations and ICH guidelines require that approval be obtained from an Institutional Review Board (IRB)/IEC before participation of human patients in research studies. Before study onset, the protocol, informed consent, advertisements to be used for the recruitment of study patients, and any other written information regarding this study intended to be provided to the patient or the patient's legally authorized representative must be approved by the IRB/IEC. Documentation of all IRB/IEC approvals will be maintained by the site and will be available for review by the Sponsor or its designee.

All IRB/IEC approvals should be signed by the IRB/IEC chairman or designee and must identify the IRB/IEC name and address, the clinical protocol by title or protocol number or both, and the date approval or a favorable opinion was granted.

The Investigator is responsible for obtaining continued review of the clinical research as specified by the IRB/IEC, at intervals not exceeding 1 year. The Investigator must supply the Sponsor or its designee with written documentation of continued review of the clinical research.

11.3 Patient Information and Consent

Informed consent in compliance with IRB/IEC and local regulations shall be obtained from each patient or their legally authorized representative before performing any study procedures and will be documented with a signed IRB/IEC approved ICF. Before enrollment, each prospective patient or his or her legally authorized representative will be given a full explanation of the study and be allowed to read the approved ICF. Once the Investigator is assured that the patient/legally authorized representative understands the implications of participating in the study, the patient/legally authorized representative will be asked to give consent to participate in the study and sign the ICF. The process for obtaining consent has to be documented at the institution.

If the ICF is revised during the course of the study, all patients on-study, including those in follow-up, must sign the revised form, unless otherwise indicated by the IRB/IEC (local or global, as applicable). In such case, the reason for not re-consenting the patient should be documented.

11.4 Confidentiality

All laboratory specimens, evaluation forms, reports, and other records will be identified in a manner designed to maintain patient confidentiality. All records will be kept in a secure storage area with limited access. Clinical information will not be released without the written permission of the patient (or the patient's legal guardian), except as necessary for monitoring and auditing by the Sponsor, its designee, regulatory authorities, or the IRB/IEC.

The Investigator and other study staff may not disclose or use for any purpose other than performance of the study any data, record, or other unpublished, confidential information disclosed to those individuals for the purpose of the study. Prior written agreement from the Sponsor or its designee must be obtained for the disclosure of any said confidential information to other parties.

11.5 Financial Disclosure and Obligations

Investigators are required to provide financial disclosure information to allow the Sponsor to submit the complete and accurate certification or disclosure statements as required under 21 CFR 54 and local regulations. In addition, the Investigator must promptly update this information if any relevant changes occur during the course of the investigation and for 1 year following the completion of the study.

11.6 Serious Adverse Events Report Requirements

The Sponsor will ensure that all relevant safety information (SAEs and SUSARs) is reported to the FDA and competent authorities of European Member States, and to the IRB/IEC, in accordance with current legislation.

11.7 Study Conduct

The Investigator will conduct all aspects of this study in accordance with the principles of the current version of ICH E6 as well as all national, state, and local laws and regulations. Study personnel involved in conducting this study will be qualified by education training and experience to perform their respective tasks. Study information from this protocol will be posted on publicly available clinical study registers before enrollment of patients begins.

11.8 Protocol Amendments

Any change in the study plan requires a protocol amendment. All amendments to the protocol must be reviewed and approved following the same process as the original protocol before the amended protocol can be implemented. The Investigator will inform the governing IRB/IEC of all protocol amendments issued by the Sponsor in accordance with established IRB/IEC procedure. Only protocol amendments intended to eliminate an apparent immediate hazard to patient(s) may be implemented immediately, i.e., without IRB/IEC approval, but the circumstances of the change must be documented and submitted to the IRB/IEC.

11.9 Monitoring of the Study

All aspects of the study will be carefully monitored by the Sponsor or designee for compliance with GCP and applicable government regulations.

Investigators and institutions involved in the study will permit study-related monitoring, audits, IRB/IEC review, and regulatory inspections by providing direct access to all study records. In the event of an audit, the Investigator agrees to allow the Sponsor, representatives of the Sponsor, or a regulatory agency access to all study records.

The Investigator should promptly notify the Sponsor and the CRO of any inspections scheduled by any regulatory authorities and promptly forward copies of any inspection reports received to the Sponsor.

11.10 Records Retention

Essential documents should be retained for at least 15 years from the completion of the study (last patient last visit) or until at least 2 years after the last approval of a marketing application in an ICH region or until there are no pending or contemplated marketing applications in an ICH region or at least 2 years have elapsed since the formal discontinuation of clinical development of the investigational study drug. However, these documents should be retained for a longer period if required by the applicable regulatory requirements or by an agreement with the Sponsor. It is the responsibility of the Sponsor to inform the Investigator/institution as to when these documents no longer need to be retained.

